7. METHODOLOGY

7.1. Study setting.

The study will be conducted in Mexico City under the sponsorship of Zélé® and in collaboration with the VIME Weight Loss and Wellness Center of Mexico. During the year 2021 and with follow-up for 24 months. An open call will be made through different media including social networks for the recruitment of patients who meet the inclusion criteria and must present themselves for a clinical evaluation in which pathological history, clinical status, heart rate, blood pressure, oxygenation and temperature will be recorded. Nutritional assessment in which anthropometry and multifrequency electrical bioimpedance analysis (MFBIA) will be performed to determine body composition. Patients will have to bring a Complete Blood Count, a biochemical profile that includes the following determinations: Fasting blood glucose, glycosylated hemoglobin, urea, creatinine and uric acid, cholesterol, triglycerides, LDL, HDL and VLDL, direct and indirect bilirubins, alanine and aspartate aminotransferases, gamma-glutamyl transferase and albumin, determination of serum electrolytes sodium, chloride, potassium, magnesium, phosphorus and calcium, Fasting Insulin , HOMA index calculation. In addition to a thyroid function panel and arterial blood gases. They will be instructed during recruitment for the studies to be performed in a clinical laboratory, under the current standardization and with standardized and perfectly calibrated automated equipment, and a request will be made to keep the vials of the patients' plasmas. Patients who meet all the inclusion criteria will be selected and will have an interview with the principal investigator in which they will sign their letter of commitment and informed consent, then they will be subjected to the randomization process with a 2:1 allocation for treatment and controls, respectively. Subsequently, they will be submitted to the two nutritional treatments and will be clinically evaluated every week and will receive nutritional, psycho emotional and physical activity counseling. At each visit, adverse effects, changes in clinical status will be recorded and the presence of ketone bodies in capillary blood will be determined with the Freestyle Abbott optium H β -Ketone (β -hydroxy-Butyric Acid) device; during nutritional counseling, MFBIA will be performed using the In-Body 570 body composition analyzer. When ketone body levels above 0.8 mmol/liter are detected, a new arterial blood gas analysis will be taken; for patients who do not have elevated ketone bodies, an arterial blood gas will be taken between the first and second week of treatment. A new biochemical profile determination will be performed when patients have lost 40% of their overweight or between 10 and 12 kg, whichever

occurs first. And new biochemical evaluations when the decrease of Ketone Bodies below 0.4 mmol/l is detected or when patients have reached a loss of 60 to 70% of their overweight and one more when they reach their weight loss goal. Subsequently, only clinical and nutritional follow-up will be given along with psycho-emotional support and physical activity advice every 3 months up to 12 months and every 6 months up to 24 months.

7.2 Study design.

Longitudinal, Prospective, Controlled Randomized Clinical Trial.

7.3 Study population.

Patients of either sex, between 18 and 60 years of age, with a body mass index (BMI) between 30 and 35 kg/m².

7.4 Sample.

The sample will be obtained by open call through social media and all patients who come with their clinical analysis and meet the inclusion criteria will be evaluated until the sample number is reached. In order to obtain 95% power in this Controlled Clinical Trial and with a 95% CI, a 3:1 case-control ratio is established, considering a 35% attrition rate, 56 cases and 32 controls will be included and subsequently crossed to become cases. (Calculated with EPIinfo STATCALC for sample size)

Two blinded arms are proposed for the physician and the patient.

Obese patients assigned to the low-fat normoprotein controlled ketogenic diet group.

Obese patients assigned to a balanced hypocaloric diet. And who will subsequently be subjected to a controlled normoproteic low-fat ketogenic diet.

7.5 Inclusion, exclusion and elimination criteria.

7.5.1 Inclusion:

- Men and Women
- 18 to 60 years of age
- With BMI between 30 and 35 Kg/m²
- Who has not taken weight loss treatment in the last 6 months

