Blood samples will be collected in Specialized Clinical Laboratories according to NOM-253-SSA1-2012 and the laboratory sample collection manual in force in each laboratory. A venous sample will be taken to determine Complete Blood Biometry, Blood Chemistry of 27 elements, Basic thyroid profile, Glycosylated

7.8 Measuring instruments.

With all the data, a database will be built in Excel MS®. Patient satisfaction will be measured with the Likert Scale, which consists of 5 possible answers per item: very satisfied, satisfied, indifferent, dissatisfied and very dissatisfied. (attached)

7.9 Statistical analysis.

Descriptive statistical tests will be performed establishing general and group measures, determining variability measures such as standard deviation and Confidence Interval, comparative inferential tests will be performed within and between groups, for quantitative variables it is proposed as an initial T-test, which will be contrasted according to the conditions of normality and homoscedasticity of the sample. For qualitative variables, χ^2 is initially proposed, which will be contrasted according to the same conditions; one-way ANOVA and repeated measures ANOVA will also be used. Microsoft Excel 365 and SPSS V 21

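### Candidates bring their own baseline blood results and nothing ties later samples to the same laboratory, so laboratory differences can enter the within-group biochemical changes and H3 and H4

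*Combined protocol and SAP*

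**What the plan says.** All references are to the combined protocol and SAP.

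- **Baseline.** Section 7.1: "Patients will have to bring a Complete Blood Count, a biochemical profile that includes the following determinations". The list covers biochemistry, fasting insulin with HOMA, lipids, liver enzymes and electrolytes, with a thyroid panel and arterial blood gases added. Section 7.4 repeats the arrangement: "all patients who come with their clinical analysis and meet the inclusion criteria will be evaluated until the sample number is reached".
- **Sequence.** Section 7.1 goes from brought-in results to selection, consent, randomisation and treatment, and then to a new biochemical profile triggered by weight loss. No other baseline draw is described.
- **Safeguards.** Section 7.1 adds "They will be instructed during recruitment for the studies to be performed in a clinical laboratory, under the current standardization" and asks for calibrated automated equipment. It also says "a request will be made to keep the vials of the patients' plasmas". No re-assay of those vials is planned.
- **Laboratories.** Section 7.7: "Blood samples will be collected in Specialized Clinical Laboratories according to NOM-253-SSA1-2012", and according to "the laboratory sample collection manual in force in each laboratory". The paragraph breaks off mid-list in the text available to us.
- **Analysis.** Section 7.9: "comparative inferential tests will be performed within and between groups". No laboratory term is mentioned.
- **Hypotheses.** In section 6, H3 (metabolic syndrome and its components) and H4 (pH and lactate) are stated for Tx1 alone, with no comparator.

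**The concern.** A change from baseline is interpretable only if both values are on the same measurement scale. Calibration inside each laboratory does not make assays agree between laboratories. Section 7.7 obliges each patient to keep to one control centre, but there is no matching rule for the laboratory. A candidate may bring a result of any age from one laboratory and have the next sample assayed elsewhere.

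Biochemical response is part of the general objective, and ionic, renal and hepatic safety are among the specific objectives (section 5). The exposed analyses are the within-group tests and H3 and H4, because a before-after change in one arm has nothing to separate a laboratory shift from a diet effect. H4 is a claim of no change, so a shift could create an apparent change or mask a real one.

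**Working it through.** The plan gives no between-laboratory or within-patient variability, so there is no figure of its own to reproduce. What follows is an illustration.

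**Inputs**
- From section 7.4: 56 patients in the ketogenic arm and 35% attrition. 56 x 0.65 = 36.4, taken as n = 36.
- Assumed, not in the documents: within-patient CV 15% to 25%; a systematic shift of 5% or 10% between the baseline and follow-up laboratories, the same for every patient; no true diet effect; two-sided 5% test on the log scale.

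**Within-group before-after test**

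SE of the mean log change = sqrt(2) x CV / sqrt(36).
- CV 15%: SE = 0.0354
- CV 25%: SE = 0.0589

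With d = ln(1 + shift)/SE, the rejection probability is Φ(d - 1.96) + Φ(-d - 1.96).

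| Shift | ln(1 + shift) | d, CV 25% | d, CV 15% | Rejection rate |
|---|---|---|---|---|
| 10% | 0.0953 | 1.62 | 2.70 | 37% to 77% |
| 5% | 0.0488 | 0.83 | 1.38 | 13% to 28% |

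The nominal rate is 5%. With a t distribution on 35 degrees of freedom, the 10% shift gives 35% to 75%. If only half the patients change laboratory, the mean shift is 0.0477, d falls to 0.81 to 1.35, and the rejection rate is about 13% to 27% (ignoring the small extra spread from mixing shifted and unshifted patients).

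**Between-arm comparison**

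The baseline sample precedes randomisation. If laboratory changes are equally common in both arms, the expected shift cancels. A simulation with shifts of 0.2 to 0.5 SD of change in both arms kept the between-arm rejection rate at 5% and the mean bias at zero.

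What remains is noise. Take an assumed within-patient CV of 20%, so the variance of change is 2 x 0.20² = 0.08, and let laboratory effects vary at random between patients:

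| Between-laboratory CV | One common follow-up laboratory: (0.08 + CV²)/0.08 | Laboratories vary at both times: (0.08 + 2CV²)/0.08 |
|---|---|---|
| 10% | 1.125 | 1.25 |
| 20% | 1.5 | 2 |

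A comparison that would otherwise have 95% power keeps Φ(3.605/sqrt(ratio) - 1.96): about 92% and 84% in the first column of ratios, 90% and 72% in the second. Patient-to-patient variation in response is left out. Including it would lower both the rejection rates and the variance ratios.

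**When the between-arm comparison could be biased**

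This needs unequal laboratory use. If, by assumption, 75% of one arm and 25% of the other changed laboratory with a shift of 0.3 to 0.5 SD of change, the bias would be 0.5 x 0.3 = 0.15 to 0.5 x 0.5 = 0.25 SD. In simulation with 36 and 21 completers the rejection rate was 8% to 14%.

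**The case against.** The strongest reply is that the trial's question is comparative and randomisation protects it. That stands. A reader might infer that the randomised biochemical comparison is biased; the documents do not support this. Baseline results precede randomisation, and nothing says that laboratory use differs by arm. Follow-up biochemistry is triggered by weight loss or ketone level, so its timing may differ by diet. That leaves a route open but does not show that it is taken.

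A reader might also infer that the plan sends follow-up samples to other laboratories than the baseline. It does not say so. Section 7.7 does not separate baseline from follow-up, may describe both, and is cut off, so a same-laboratory rule could be in the lost text. Treating the brought-in profile as the baseline is itself an inference, though a strong one given the sequence in section 7.1. The point is that the visible text allows a mismatch, not that one is planned.

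The equipment instruction and the plasma request also count in the plan's favour. Stored plasma could allow paired re-assay of stable analytes. But no re-assay is planned, and it could not replace arterial blood gases, on which H4 depends.

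Finally, the rejection rates assume that every patient shifts in the same direction by the same amount. If candidates use many laboratories, shifts partly cancel and the problem moves from bias towards noise.

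**Conclusion.** The point holds, limited to within-group biochemical changes and to H3 and H4. As visible, the plan permits baseline and follow-up values from different laboratories and sets no limit on the age of the baseline. On the assumptions above, a uniform 10% shift would produce a significant before-after result in about 37-77% of trials with no diet effect, and a 5% shift in about 13-28%; both are lower if only some patients are affected. The between-arm comparison loses precision (variance of change up 1.125- to 2-fold, depending on the assumed laboratory variability and on whether follow-up shares one laboratory) but is not biased in expectation unless laboratory use differs by arm. Weight, bioimpedance and capillary ketones are measured at study visits, so H1 and H5 are untouched. The CVs and shifts are all assumptions, and the sizes show what is possible, not what will occur. The matter should be settled before recruitment, because a comparable baseline cannot be drawn once the diet has begun.

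**What to change.** - In the recruitment instruction in section 7.1, direct all candidates to one named study laboratory, and use it for the baseline and every later sample. One laboratory per control centre would not work for the baseline, because section 7.7 assigns the centre only after patients are drawn by lot.
- State a maximum interval from baseline sample to randomisation.
- Record laboratory and sample date for every result.
- Use a result from elsewhere, or from outside the window, for eligibility only.
- In section 7.9, base biochemical conclusions on the baseline-adjusted between-arm comparison, and present within-group changes as descriptive.

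**Cost.** Some inconvenience for candidates, two data fields, and possibly a repeat test for those who arrive with outside results. Section 9.1 has a laboratory line of $572,184.00 but does not say whether entry tests are covered, so this should be checked.

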5. OBJECTIVES

5.1 *General Objective*

To evaluate differences in the response of weight, body composition and metabolic biochemical parameters among obese patients following a normoprotein low-fat controlled ketogenic diet compared to a balanced BIEM).

5.2 *Specific Objectives*

- Intra- and intergroup comparison of patient weight and BMI reduction between baseline and subsequent follow-up monitoring visits.
- To determine the percentage of patients with weight loss equal to or greater than 10% of initial weight and the time it took for patients to reach this figure.
- Evaluate the evolution of comorbidities associated with obesity (HT, hyperglycemia or diabetes, hypercholesterolemia, hypertriglyceridemia, apneas), control of clinical and analytical parameters and changes in medication during the weight loss process and during follow-up.
- To know the tolerability of the diet: Incidence of side effects during the development of the study,
- Safety of the intervention diet: appearance of analytical alterations, especially of the ionic profile, renal function and hepatic function, incidence of serious adverse events.
- Assess diet adherence and dropout rate and cause.
- To know patient satisfaction with the assigned nutritional program.

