6. HYPOTHESIS

Assumption 1: **Weight Loss** .

H1: The use of the "Zélé method" (**Tx1**) allows a greater weight loss (*pp*) than a hypocaloric diet (**Tx2**) in the same time (*t*).

Assumption 2.

H2: Tx1 is safe and with low or no adverse effects.

Assumption 3. **Metabolic conditions**

H3: *pp* with Tx1 allows the regulation of metabolic syndrome and its components.

H4: The state of controlled ketosis that occurs with Tx1 does not change pH or raise blood lactate levels.

Assumption 4 . **Body Composition**.

H5. Tx1 will produce a selective loss of fat and preservation of muscle mass.

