Arterial pH	Indicates the amount of hydrogen ions contained in the blood.	Determines the degree of acidity or alkalinity of the blood.	Quantitative, Ratio minimum 7.35 maximum 7.45	Registration form. Blood analysis
Lactic Acid	Substance produced by muscle tissue and blood cells. Lactic acid levels increase when oxygen levels decrease.	Acidic substance that accumulates in the blood and causes a decrease in pH, its ionized form is lactate.	Quantitative, Ratio 4.5 to 19 mg/l or 0.5 to 2.2 mmol/liter.	Registration form. Blood analysis
Anion Gap	Difference between anions and cations measured in the serum	Difference between anions and cations measured in serum	Quantitative, Ratio unit mEq/l minimum 8 max. 12	Registration form. Blood analysis
Excess Base	the amount of acid required to return the pH of an individual's blood to a normal value	the amount of acid required to return the pH of an individual's blood to a normal value	Quantitative, Ratio Minimum -2 maximum + 2	Registration form. Blood analysis

Satisfaction and Adherence				
Satisfaction Survey	Positive assessment of the different dimensions of the medical care received	Interrogation Very Satisfied to Very Dissatisfied	Categorical Nominal	Registration form.
Adherence to treatment	Taking medication according to the dosage of the prescribed schedule; and persistence, taking medication over time.	Interrogation Complied or did not comply with the program.	Categorical Nominal	Registration form. adherence to treatment

7.7 Data collection.

All data will be captured and recorded digitally in each of the queries through the Google Forms platform to consolidate the information in Google Sheets.

In the consultation, medical history data will be collected in the form of interrogation, weight will be determined through electronic scales, height through calibrated stadiometers, All measurements will be performed according to the WHO Physical Measurement Guide 2014 (www.who.int/surveillance/steps/Part3_Section4) Annex 1. In addition, a capillary determination of glucose and ketones will be performed at each clinical consultation. Once patients are drawn by lot they will be assigned to one of the control centers distributed in Mexico City, they will always have to go to the same control center (VIME). The consultation visits will be weekly for weight control and clinical check-up and every two weeks alternately for physical and psychological counseling.

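### Side effects are recorded at visits that appear to thin out once a patient reaches goal weight, so a whole-study comparison between arms may favour the ketogenic diet for mild effects

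*Combined protocol and SAP*

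**What the plan says.** Section 7.1 ties the collection of side effects to attendance: "At each visit, adverse effects, changes in clinical status will be recorded". During treatment, patients in both arms "will be clinically evaluated every week". The same section then sets biochemical evaluations at weight-loss milestones, the last of them in these words: "one more when they reach their weight loss goal. Subsequently, only clinical and nutritional follow-up will be given". That later follow-up runs "every 3 months up to 12 months and every 6 months up to 24 months". No calendar date ends the weekly phase, and no schedule is given for a patient who never reaches goal. Section 7.7 says "The consultation visits will be weekly for weight control and clinical check-up" and gives no end point.

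H1 in section 6 states that the ketogenic programme "allows a greater weight loss (*pp*) than a hypocaloric diet" over the same time. Section 5.2 words the tolerability objective as "To know the tolerability of the diet: Incidence of side effects during the development of the study". Section 7.9 plans tests within and between groups, with chi-square as the first proposal for qualitative variables. It does not mention adverse effects, a window for them, person-time or number of visits. Section 7.4 has the 32 controls cross to the ketogenic diet later, at a time not stated.

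**The concern.** How often a patient is asked about side effects appears to depend on when that patient reaches goal weight. That is an outcome after randomisation, and the trial's own hypothesis expects it to differ between arms, so randomisation does not balance it. If the ketogenic arm reaches goal sooner, its patients move sooner to visits three or six months apart, and a mild effect that came and went between visits is less likely to be reported. With equal true risks, the recorded incidence would then be lower on the ketogenic diet, and the gap would widen as the difference in goal times widened.

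At stake is the reading of the tolerability result. A favourable comparison over the whole study could not be separated from less frequent questioning.

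**Working it through.** The plan gives no adverse-event rate, expected goal time or visit count, so there is no stated figure to reproduce. The calculation below is illustrative.

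**Inputs from the plan.** 56 and 32 patients (7.4); weekly visits to goal, then visits at months 3, 6, 9 and 12 (7.1), taken as weeks 13, 26, 39 and 52 from baseline.

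**Assumptions.** The weekly phase lasts 12 or 16 weeks (ketogenic) v 26 weeks (control). The true weekly risk h is 1% or 2% in both arms. An event is reported at the next visit with probability exp(−lag/τ), with τ from 4 to 26 weeks. There is no crossover or dropout before month 12.

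**Visits to month 12.** Ketogenic, 12-week phase: 12 + 4 = 16. Ketogenic, 16-week phase: 16 + 3 = 19. Control: 26 + 2 = 28.

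**Formula.** With λ = −ln(1−h) and gaps L between successive visits, the expected number of recorded events per patient is m = λτ·Σ(1−exp(−L/τ)). The proportion of patients with at least one recorded event is 1−exp(−m).

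**Worked case: h = 2%, τ = 4, 12 v 26 weeks.** λτ = 0.0202 × 4 = 0.0808. A one-week gap contributes 1−exp(−0.25) = 0.2212; a 13-week gap contributes 1−exp(−3.25) = 0.9612.
- Ketogenic: 13 × 0.2212 + 3 × 0.9612 = 5.759; m = 0.465; recorded 37.2%.
- Control: 26 × 0.2212 + 2 × 0.9612 = 7.674; m = 0.620; recorded 46.2%.
- Apparent risk ratio: 37.2/46.2 = 0.81. True risk in both arms: 1−0.98^52 = 65%.

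The chance that an uncorrected chi-square test (two-sided 5%) favours the ketogenic arm comes from enumerating both binomials (56 and 32).

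| h per week | Weekly phase (weeks) | τ (weeks) | Recorded | Risk ratio | Falsely favours ketogenic |
|---|---|---|---|---|---|
| 1% | 12 v 26 | 4 | 20.7% v 26.5% | 0.78 | 10% |
| 2% | 12 v 26 | 4 | 37.2% v 46.2% | 0.81 | 13% |
| 2% | 12 v 26 | 8 | 47.1% v 52.9% | 0.89 | 8% |
| 1% | 16 v 26 | 26 | 36.0% v 37.0% | 0.97 | 3% |
| 2% | 16 v 26 | 26 | 59.3% v 60.5% | 0.98 | 3% |
| 1–2% | either | complete recall | equal | 1.00 | about 2.5% |

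**Sensitivity.**
- *Goal times.* At 20 v 26 weeks, with h of 1–2% and τ of 4–26, the ratio is 0.94–0.99 and false significance about 3–4%. At 17 v 35 weeks, with one event per patient-year (1.9% per week) and τ = 4, 39.7% v 51.2% is recorded, a ratio of 0.78 with false significance of 18%; at τ = 8 it is 10%.
- *Timing of events.* If the hazard decays with a mean of 6 weeks, the ratio of recorded events to month 12 is 0.92–0.99, for goal times of 13 v 26 to 26 v 52 weeks and τ of 4–13.
- *Common window.* Over the first three months with both arms still weekly, each arm has 13 visits and the ratio is 1.00 at every τ.

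**Upper bound for these goal times.** If nothing were recorded after the weekly phase, the proportion would be 1−(1−h)^weeks. At 2% this gives 21.5–27.6% v 40.9%, a ratio of 0.53–0.68 and false significance of 25–50%; at 1%, false significance is 18–33%.

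**The case against.** The strongest reply is that the bias is conditional and its direction is not assured.

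- *Later visits still collect side effects.* This stands. A reader might infer that questioning stops at goal and so arrive at 25–50% false significance, but 7.1 keeps clinical visits to month 24 and records adverse effects at every visit. Those figures are only a bound.
- *Twelve to sixteen weeks is a short time to goal.* This stands. Section 2 proposes two to three months for the ketogenic stage alone, with the transition and integral stages to follow. Section 7.10.1 sets no time for frank ketosis. The 26 weeks for controls has no source in the plan.
- *No between-arm test of side effects is specified.* Largely right. Section 7.9 never names adverse effects, and H2 concerns the ketogenic diet alone. But 7.9 does plan between-group tests in general, and under-recording would also help H2's claim of few or no adverse effects.
- *Other routes capture events.* Section 7.5.3 requires immediate reporting of adverse reactions, and serious or lasting events are less easily forgotten. That limits the point to mild, transient effects, because 7.5.3 schedules no questioning between visits.
- *Laboratory safety could go the other way.* Biochemistry follows weight-loss milestones and extra blood gases follow raised ketones, so the ketogenic arm may be tested more.
- *Crossover may reverse the direction.* If control time stops at crossover, controls may be observed for less time. If it does not, their later events occur on the ketogenic diet. Both possibilities are open, and both argue against a whole-study comparison.
- *The step-down is inferred.* It rests on the order of sentences in 7.1, and 7.7 gives no end to weekly visits.

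**Conclusion.** The point holds as a conditional gap in specification. Read naturally, the plan makes the intensity of questioning depend on an outcome that H1 expects to differ by arm, takes incidence over the whole study, and provides no correction. A between-arm comparison made that way may favour the ketogenic diet for mild effects elicited at visits.

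Under the tabulated assumptions the apparent risk ratio is about 0.78–0.98, and false significance favouring the ketogenic arm is about 3–13% against a nominal 2.5% or so. Closer goal times, early events or better recall bring it towards no bias; goal times further apart increase it. None of these inputs is given in the plan.

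A reader might conclude that the ketogenic arm will look safer overall. The documents do not support that: it requires H1 to hold, recall to be imperfect and the comparison to run beyond the shared weekly phase. Laboratory monitoring and crossover could also act in the opposite direction.

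**What to change.** First reconcile 7.1 and 7.7 on when weekly visits end, including for patients who do not reach goal, and state when controls cross over.

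Then add to 7.9:
- The main between-arm comparison of tolerability covers one fixed window from randomisation, before any crossover and while both arms are seen weekly. The first 12 weeks would serve, once it is confirmed that both arms are still weekly throughout. All randomised patients are counted, including those withdrawn under 7.5.3.
- Later events are reported separately as rates per person-time with confidence intervals, by visit phase and by diet actually received, with the number of visits per arm.

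This costs analysis wording and needs no new data. The downside is that events after the window become descriptive only, and the window holds fewer events: at the illustrative 1–2% per week, 1−0.99^12 = 11% to 1−0.98^12 = 22% of patients would have one within 12 weeks.
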